Study Title: A Partnership to Translate an Evidence-based Intervention (Take Heart) for Vulnerable Older Adults with Heart Disease

NCT02950818

3/21/2019

This document discusses methodologies for both the pilot study and the portion of the main study that will be conducted with participants recruited through the Detroit Area Agency on Aging, other community sources, the UM Institute of Gerontology database, or the UMClinicalStudies.org website. We have indicated which information applies to the pilot study, the main study or both.

ROLES/RESPONSIBILITIES OF STUDY PARTNERS:

Focus groups, Pilot and Main Study

The UM Center for Managing Chronic Disease (CMCD) is responsible for contacting, screening and enrolling participants (based on lists of names of interested individuals provided by DAAA or who call the project hotline directly after seeing flyers or other advertisements). CMCD is responsible for survey data collection, data storage and management, and analysis. CMCD will train the DAAA-affiliated health educators to deliver the intervention and will provide oversight and technical assistance. CMCD is also responsible for all reporting to funder and for managing subcontracts.

The Detroit Area Agency on Aging (DAAA) will be responsible for delivering the intervention to participants, under direction from the Center for Managing Chronic Disease. They will also be responsible for scheduling participants into sessions, and collecting attendance and other process data, such as topics covered in intervention sessions. They will also engage in some limited recruitment activities (e.g., posting flyers). NOTE: These activities will be overseen by the UM IRB, as DAAA does not have their own IRB.

The Detroit Medical Center (Rosa Parks Geriatric Center) will be responsible for the following: Identifying potential participants based on specific ICD-10 codes from electronic medical records, and sending these lists securely to CMCD. They are also responsible for extracting health care utilization data at two time points (baseline and 12 months) from electronic medical records of participants who provide consent for this. Finally, if deemed convenient for participants by the Community Working Group (an advisory group for the project), DMC may host some intervention sessions (led by DAAA staff) on site at their medical campus.

Recruitment Flowchart

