Participants assigned to the Take Heart Program Group will be asked to talk to a health educator/heart disease counselor 2 times over the phone, and 5 times in person as part of a group. Health educators will be trained DAAA staff members, and will have background/experience in health promotion, health education, health coaching, or related areas but will not necessarily have clinical training. There are 7 total combined phone and group education sessions over a total of 7 weeks during which they will learn ways to manage heart disease. More information about the program content and process is found in the Study Background document. Each telephone session will be 30-50 minutes, and each group session will last 120-180 minutes. Telephone sessions will be audio recorded for guality assurance purposes. Participants will also be provided a binder of materials as part of this program. After completing the 7 weeks of groups and phone sessions, the health educator will check in with each participant 3 more times throughout the course of the year, at the 3, 6 and 9-month marks. Two of these check ins will be via mail (3 months and 9 months); each participant will receive a Take Heart newsletter tailored to the main topic of their goals. The 6-month check in will be via phone; the health educator will call each participant to follow up with them, check in on their goals and answer any questions they may have at that time. This phone call will also be audio recorded. These check-ins are intended to help keep participants motivated to continue working on their goals and remind them of their participation in the Take Heart program. Individuals in the waitlist/control group will receive usual care. If time and funding allows they will have the opportunity to participate in the Take Heart intervention once they have completed their followup (12-month) survey.

DATA COLLECTION:

Pilot Study

Data sources for the pilot study include: (1) CMCD observer notes from the education sessions; (2) qualitative data gathered through the participant debrief; and (4) quantitative and qualitative data gathered from the pilot-test of the baseline questionnaire.

Observer notes: at each education session a member of the CMCD research will be present taking notes about session activities and participant response.

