Participant debrief: Participants will be asked the following questions regarding their satisfaction with various program topics and elements, in a group format or, if preferred by participants, oneon-one: What did you like about this element/activity/topic? What could we do to make it better? They will also be asked: Is there anything else that should be in the program that is not? How well do you feel like the program addressed your needs? What can we do to keep participants' interest in the program? Did you use the materials—why/why not and how?

Note that this data is for purposes of program refinement.

Pilot-Test Baseline Survey: We will pilot-test our baseline survey to see what areas, if any, of the survey need adjustment before we begin the RCT. We will also ask up to 10 participants who agree to pilot the survey to answer check-in questions about their experience with the survey every 2-3 pages. This will allow us to gather more detailed information about what areas of the survey can be improved. We have uploaded the feedback questions we plan to ask in Section 29.

From the audio recordings we will transcribe participant answers to the feedback questions; and record information about length of the survey and participant engagement with interviewer. An alpha-numeric participant ID will be used in all transcribed materials to protect the individuals' identity.

Note that this data is for purposes of survey refinement.

Main Study

Data sources for this study include: (1) participant telephone surveys at two time points: baseline and 12 months; and (2) health educator logs indicating sessions attended and participation in intervention activities (copy uploaded to Section 44).

Telephone surveys: These will be conducted by trained research assistants, and will collect health, psychosocial, and demographic data. The vast majority of measures used in this study are standard measures that have been used in previous studies. A copy of the survey is uploaded in Section 29. A copy of our Interviewing Protocol, which includes a description of interviewer training and oversight, is uploaded in Section 44. Telephone surveys will be audio recorded for quality assurance.

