Health educator logs and session observation: The 'dose' of the intervention will be examined using the logs completed by the health educator. The subject will receive one point for each of 4 sessions attended and a point for each of the three components completed: goal setting, tracking form, and the judgment/reaction. The scores will only be available for the intervention group and will describe average level of participation within the intervention group using frequencies and mean scores. The components of the intervention: observation, judgment, goal setting strategies, outcome expectancy and efficacy can also be described individually.

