Intervention fidelity will be assessed at two levels. The first level will compare the adapted with the original program. A second level of fidelity assessment, employed in previous work by the CMCD, will examine how the adapted program is implemented by DAAA. Those charged with delivering the adapted program may not maintain full fidelity or protocols may need to change mid-stream in response to unanticipated issues. The CMCD will assess fidelity in partnership with DAAA and RPC personnel. At the end of each session, the health educator will fill out a "fidelity checklist', summarizing delivery of the core components of the program: teaching the "PRIDE" problem solving process, number of sessions attended, observation tools distribution, and an interactive discussion format. CMCD staff will observe a randomly-selected subset of "take PRIDE" sessions to assess coverage of core components and other key intervention processes, using a standardized rating form. The proposed study team has employed fidelity tools and logs for clinical trials that have informed the development of these draft tools; they will be further refined for this project and tested during the pilot-study in Aim 1. A qualitative and contextual approach to fidelity will be employed through a systematic ongoing process assessment. This will include annual in-depth interviews with key stakeholders (staff). These interviews will explore and document the barriers and facilitating factors experienced in terms of program implementation, as per Specific Aim 3 of the study - ""Assess the process of translation and implementation of the intervention in the target setting and identify factors that help or hinder the process." Interview protocols for staff will be developed to explore perspective and meaning about implementation; (e.g., reasons for adaptation). These protocols will be based on those developed for previous CMCD dissemination projects but will be refined for the current project.

DATA STORAGE:

Focus groups:

The following steps will ensure that participants' privacy will be maintained:

1) No names or other identifying information will be included in the transcribed focus group discussions, and thus no information will be included in any published or unpublished reports using interview data that could be used to identify any participant.

2) Participants' names will not be included on the short supplemental written survey; these will be anonymous.

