Intervention dose received: The dose of the intervention will be examined using the logs completed by the health educator. The subject will receive one point for each of 4 sessions attended and a point for each of the three components completed: goal setting, tracking form, and the judgment/reaction. The scores will only be available for the intervention group and will describe average level of participation within the intervention group using frequencies and mean scores.

The components of the intervention: Observation, judgment, goal setting strategies, outcome expectancy and efficacy can also be described individually. Participants in the intervention group may be stratified based on the dose score and outcomes compared using t-tests or chi-square tests of homogeneity to describe impact of dose on outcomes. Instrumental variable approaches to estimating the complier-average causal effect of the intervention will be applied, with compliance defined using two different choices of cut-off on the performance score.

Change over time: The focus of the mixed-model (for continuous outcomes) and GEE (for discrete outcomes) analyses will be to assess changes in dependent measures over time, and whether these changes differ between program participants and "usual care" controls. The effect of time as well as the interaction between time and program participation (program vs. waitlist control) will be included as factors in all models.

Generalizability of the intervention: To determine how effective the intervention would be if duplicated in a similar population, it will be important to examine non-consenters to see if those who choose to participate have certain factors that may be correlated with improved outcomes not present in those who do not participate. Aggregate data from the DMC including demographics, and health care use values will be obtained on those patients that meet the criteria for participation but were not enrolled in the randomized controlled trial to be compared to enrolled participants using t-tests and chi-square tests to discover any differences.

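### The dose score credits 4 sessions but the main study delivers 7, so participation and, at some cut-offs, the complier share depend on an unstated scoring rule

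*Combined protocol and SAP*

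**What the plan says.** The combined protocol and SAP gives the main-study programme under What Happens to Subjects During Research, Main Study. Participants speak with a health educator "2 times over the phone, and 5 times in person as part of a group", and the total is confirmed: "There are 7 total combined phone and group education sessions over a total of 7 weeks". The two types differ in length: "Each telephone session will be 30-50 minutes, and each group session will last 120-180 minutes". Three later check-ins (3, 6 and 9 months) come after these sessions.

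The scoring rule appears twice. Data Collection, Main Study (health educator logs and session observation) has "The subject will receive one point for each of 4 sessions attended", plus a point for each of three components. Analysis of patient outcomes (intervention dose received) repeats it: "The subject will receive one point for each of 4 sessions attended and a point for each of the three components completed". Neither place says which four sessions count, whether telephone sessions count, or whether points stop at four.

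The dose section gives the score three uses:
- It will summarise participation in the intervention arm by means and frequencies.
- It may be used to stratify that arm for comparing outcomes.
- An instrumental-variable CACE is planned, with compliance set by two cut-offs on what the plan calls the performance score. Neither cut-off is given. That this is the dose score is an inference; no other score is described.

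**The concern.** Four is not the main-study total (7), the group count (5) or the telephone count (2). It equals the number of group sessions in the pilot, so it may have been carried over, but the plan does not say so.

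Followed as written, the rule leaves some attended sessions uncredited. How this shows up depends on the reading:
- **(a) Any four of the 7.** The score is capped and cannot separate 4 of 7 from 7 of 7.
- **(b) Four specified sessions.** Three sessions earn nothing, and individuals can be misranked.
- **(c) Any four of the 5 group sessions.** One group session in five is uncredited, and telephone sessions earn nothing.

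Participation would then be reported on a scale that does not fit the programme delivered. If the score also defines compliance, its reading enters the denominator of the CACE.

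**Working it through.** **Count.** 2 + 5 = 7, which reproduces the stated total. The rule implies a maximum of 4 + 3 = 7 points; this equals the number of sessions only by coincidence.

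**Assumptions (none is in the documents).** Let K be the number of sessions attended out of 7.
- Uniform: P(K = k) = 0.125 for k = 0 to 7. Mean attendance is 3.5/7 = 50%.
- Skewed high: P(K = 0..7) = 0.10, 0.05, 0.05, 0.08, 0.10, 0.15, 0.22, 0.25. Mean attendance is 4.61/7 = 66%.
- Attendance is exchangeable across sessions, so credited sessions given K are hypergeometric.
- Each of the three components is completed with probability 0.5, independently. With C the component points, P(C = 0..3) = 0.125, 0.375, 0.375, 0.125.

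**Session points S under each reading.**

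| Attendance | Reading | S=0 | S=1 | S=2 | S=3 | S=4 |
|---|---|---|---|---|---|---|
| Uniform | (a) | 0.125 | 0.125 | 0.125 | 0.125 | 0.500 |
| Uniform | (b) | 0.200 | 0.200 | 0.200 | 0.200 | 0.200 |
| Uniform | (c) | 0.167 | 0.167 | 0.167 | 0.167 | 0.333 |
| Skewed | (a) | 0.100 | 0.050 | 0.050 | 0.080 | 0.720 |
| Skewed | (b) | 0.131 | 0.096 | 0.150 | 0.255 | 0.369 |
| Skewed | (c) | 0.117 | 0.071 | 0.098 | 0.151 | 0.563 |

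**Describing participation.**
- Reading (a): the mean session score is E[min(K,4)]/4. Uniform: (0 + 1 + 2 + 3 + 4×4)/8/4 = 0.69, against true attendance of 0.50. Skewed: (0.05 + 0.10 + 0.24 + 4×0.72)/4 = 0.82, against 0.66. Of pairs of participants with different attendance, 21% / 45% (uniform / skewed) tie on session points.
- Reading (b): the mean equals true attendance, but only if attendance is the same across sessions. If attendance fell evenly from 95% to 45% over the seven sessions, the true mean would be 70%, while crediting the first four would give (95 + 86.7 + 78.3 + 70)/4 = 82.5%. Ranking can also fail: someone who attends 6 sessions but misses a credited one scores 3, while someone who attends only the four credited sessions scores 4.

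**Complier share on the total score S + C.** The control arm has usual care until after the 12-month survey, so the complier share is the proportion of the intervention arm at or above the cut-off.
- P(total ≥ 2) = 1 − 0.5·P(S=0) − 0.125·P(S=1)
- P(total ≥ 5) = 0.125·P(S=2) + 0.5·P(S=3) + 0.875·P(S=4)

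Examples with uniform attendance at ≥ 5: (a) 0.0156 + 0.0625 + 0.4375 = 0.516; (b) 0.2 × 1.5 = 0.300.

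| Cut-off | Attendance | (a) | (b) | (c) | Highest/lowest |
|---|---|---|---|---|---|
| ≥ 2 | Uniform | 0.92 | 0.88 | 0.90 | 1.05 |
| ≥ 2 | Skewed | 0.94 | 0.92 | 0.93 | 1.02 |
| ≥ 5 | Uniform | 0.52 | 0.30 | 0.40 | 1.7 |
| ≥ 5 | Skewed | 0.68 | 0.47 | 0.58 | 1.4 |

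**CACE.** CACE = intention-to-treat effect / complier share. Taking the 0.15 difference in ED visits from Sample Size Determination as the effect, at ≥ 5 with uniform attendance: (a) 0.15/0.516 = 0.29; (c) 0.15/0.396 = 0.38; (b) 0.15/0.300 = 0.50.

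**Cut-off against reading.** Under (a) with uniform attendance, moving the cut-off from ≥ 2 to ≥ 5 lowers the share by 0.92 − 0.52 = 0.40, whereas changing the reading at ≥ 5 moves it by at most 0.52 − 0.30 = 0.22. Over all cut-offs from 1 to 7, the share under (a) runs from 1 − 0.125 × 0.125 = 0.98 to 0.500 × 0.125 = 0.06.

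**The case against.** The best reply is that little rests on this.
- Only descriptive and supplementary analyses use the score.
- The log form is filed separately and may name the four sessions. Programme content is referred to a background document, and the fidelity tools and logs are called drafts to be refined.
- If the number came from the pilot's group sessions, reading (c) is the likely intent and the gap is one session in five.
- The missing cut-offs would leave the complier share undefined even with the session count corrected.
- Every figure above rests on assumed attendance and completion.

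All of this stands as a limit on size. It does not remove the contradiction: a form elsewhere could say which sessions count, but the two scoring statements would still not fit the main-study description in the same document.

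A reader might infer more than the documents support:
- **That the primary results are affected.** They are not; the randomised comparisons do not use the score.
- **That participation will be misstated in a known direction.** The direction depends on the reading and on how attendance varies over the sessions.
- **That the share with full session marks (20% to 50% uniform, 37% to 72% skewed) is a complier share.** It is not: the apparent cut-offs are on a total that includes three component points.
- **That the pilot carry-over is established.** It is plausible only.

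**Conclusion.** The point holds in limited form. The scoring rule, stated twice in current main-study text, credits four sessions for a programme described as having seven. As written it leaves attended sessions uncredited.

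The effect on the CACE depends on cut-offs that the plan does not give. Under the stated assumptions it is negligible at ≥ 2 and about 1.7-fold (uniform) or 1.4-fold (skewed) at ≥ 5. These figures show sensitivity and do not forecast the trial's result. The link to the CACE further rests on reading the performance score as the dose score. The change should be made because the rule is wrong as written and rescoring is cheap, even though no primary analysis is at risk.

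**What to change.** 1. Reconcile the main-study programme description with the two statements of the scoring rule, on the number and type of sessions.
2. Then credit every scheduled main-study education session recorded in the educator logs. If the seven-session description stands, the maximum is 7 + 3 = 10. The 3-, 6- and 9-month check-ins are not among the seven and earn no point.
3. Report telephone attendance, group attendance and component points separately.
4. State that this score defines compliance for the CACE, and set both cut-offs on the corrected scale before outcome data are analysed.

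**Cost.** A short change to the text and the scoring formula. No new data should be needed. Under Roles/Responsibilities, the agency delivering the programme is already charged with "collecting attendance and other process data, such as topics covered in intervention sessions"; the educator logs are described as "indicating sessions attended and participation in intervention activities"; and the fidelity checklist covers "number of sessions attended, observation tools distribution". The log form was not available to confirm its layout.

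**Downsides.** Telephone and group sessions get equal weight despite their different lengths, and the components' share of the maximum falls from 3/7 (43%) to 3/10 (30%). The separate reporting in step 3 addresses both.

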[name] from the DMC will collaborate with the DMC IT team to conduct regular data pulls from the electronic medical record of patients meeting the inclusion criteria, with the understanding that this study has an approved waiver of informed consent from the Wayne State University and University of Michigan IRBs. No sensitive medical information, other than the fact that the patient meets the specific study criteria and contact information, will be accessed. DMC physician Fellows will proceed to further review medical records results from ICD-10 pulls to determine likely study participant eligibility, and will be trained to look for exclusion criteria and indicators that patient would not benefit from program. Secondary review by a DMC Fellow and the DMC Data Coordinator, if needed, will further ensure eligibility before sending lists of prospective participants to CMCD. DMC staff will upload a password-protected MS Excel file to M+Box for access by UM/CMCD project director. CMCD will store patient data within the password-protected RedCap database.

Eligible patients will be mailed a recruitment package that includes a personalized cover letter from the study's principal investigators indicating collaboration with their physician as part of DMC, an information sheet describing the study and decline postcard. All recruitment packages and telephone contacts will originate from the CMCD project office to ensure patients are provided with accurate and consistent contact information about the study. The use of a recruitment script, including brief screening items, during telephone contact ensures that all potential participants receive standardized information regarding the study.

Based on previous studies involving participants from similar demographic and socioeconomic groups, we anticipate that 25-30% of those invited to take part in the study will agree to participate. Recognizing that the population of patients targeted for enrollment in the proposed research will be, on average, managing various significant psychosocial challenges and comorbidities, a conservative enrollment figure of 30% is anticipated for purposes of planning. The estimated number of patients available within the DMC is adequate to reach the figure required by our sample size determination (n=376 at baseline).

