Additionally, a postcard will be included in the recruitment package for each patient to return to the project director should they not want to be contacted by the researchers. The cover letter will also inform the patient that if they do not decline participation, they will receive a telephone call from a member of the research team to describe the study and determine their interest in participating.

These potential participants will not be asked directly about the presence of terminal illness with a prognosis of a year or less (an exclusion criterion that will be applied when DMC is screening EMR), as it is assumed that people who pro-actively call in to inquire about the program feel that they could benefit from the it and would not have a severely life-limiting illness.

Eligibility criteria for participants are as follows:

- 50 years or older
- One or more diagnosed cardiovascular conditions, including:
 - Atrial fibrillation

- Angina
- Myocardial infarction
- Congestive heart failure
- Valvular disease (aortic stenosis or mitral regurgitation)
- Peripheral vascular disease
- Pulmonary hypertension
- OR >2 major risk factors for CVD (high cholesterol, high blood pressure, smoking, diabetes, chronic kidney disease-stage 3 or 4)
- Must have access to a mobile or landline telephone
- Must be able to travel to group sessions, with or without transportation assistance

Exclusion Criteria

Limited fluency in English posing significant barrier to deriving program benefit

Screening, consent, and enrollment procedures:

Focus groups: Screening and enrollment procedures are described above. We will ask participants to sign informed consent, including consent to audio record, on site at the group, and will go over the form together as a group.

Pilot Study

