Throughout recruitment calls, each patient will be encouraged to ask questions and told that they are free to withdraw from the study at any time, for any reason. A toll-free [contact]) will be provided so that potential participants can call the research office with additional questions at any time.

Randomization will be stratified by four categories of a risk score based on data from prior studies that includes age, gender, and number of comorbidities, using responses from the baseline interview. To reduce the predictability and resulting bias due to block randomization, random block sizes (e.g., lengths of 8, 10, 12 subjects) will be used and blinded to investigators. Prior to recruitment, a permuted block randomization schedule will be created using the RANTBL and RANUNI functions in SAS to generate blocks with varying sizes of 8, 10, or 12 and random numbers for group assignment within each of the 4 categories of risk score.

Once enrolled, participants recruited through the Detroit Medical Center (DMC), will be asked to complete another consent document that includes a HIPAA Authorization statement. This will authorize DMC to release specific health information related to Take Heart after the recruitment phase (first, middle and last name, street address, city, state, zip code, email address, home and cell phone number, primary care provider and specialist, number of visits to the emergency department and hospitalizations during the year prior to the Take Heart study and the year of your participation in the study), to the University of Michigan School of Public Health research staff.

WHAT HAPPENS TO SUBJECTS DURING RESEARCH:

Focus groups:

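### The optional comparison of outcomes between dose strata within the intervention arm is worded as the impact of dose, but it is unadjusted for self-selection and can show a difference when the program has no effect

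*Combined protocol and SAP*

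**What the plan says.** The relevant text is the paragraph on intervention dose received, under Analysis of patient outcomes.

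- **The score.** "The subject will receive one point for each of 4 sessions attended", and three further points are available for program components completed, so it runs from 0 to 7. "The scores will only be available for the intervention group".
- **The comparison.** "Participants in the intervention group may be stratified based on the dose score", with "outcomes compared using t-tests or chi-square tests of homogeneity to describe impact of dose on outcomes". No covariate is named and there is no caveat about who attends.
- **The next sentence.** "Instrumental variable approaches to estimating the complier-average causal effect of the intervention will be applied", with compliance defined at two cut-offs on the score.

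Three other places bear on it. The recruitment section describes the target patients as "managing various significant psychosocial challenges and comorbidities". The eligibility list says "Must be able to travel to group sessions, with or without transportation assistance". The main-study enrolment section says "Randomization will be stratified by four categories of a risk score", built from age, gender and comorbidity count, so a baseline prognostic variable is held for everyone.

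**The concern.** Participants determine their own dose after randomization, and the control arm has no score. High-dose and low-dose strata are therefore not randomized groups, and nothing in the test makes them comparable. Comorbidity and the need to travel are plausible reasons for missing sessions, and comorbidity is also a plausible reason for ED visits and admissions, the primary outcomes. An admission during the 7 weeks of sessions could also lower the score directly, if the outcome year includes those weeks.

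The plan recognises the same issue elsewhere: its generalizability paragraph wants to know whether people who choose to join differ in ways linked to better outcomes. It does not apply that reasoning to people who choose to attend.

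What is at stake is interpretation. If the randomized comparison were null, a significant difference between dose strata, described in advance as the impact of dose, could be reported as evidence that attendance works.

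**Working it through.** **Figures in the plan.** There is none for this comparison. The nearest is 188 per arm to detect a difference of 0.15 in the change in ED visits. It cannot be checked, because SD, alpha, sidedness and power are not given. At two-sided 5% and 80% power it implies an SD of change of 0.15 / [(1.96 + 0.84) × √(2/188)] = 0.52.

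**Inputs.** From the documents: 376 enrolled, so 188 per arm; about 20% loss, so 188 × 0.80 ≈ 150 with follow-up; a score of 4 + 3 = 7 points. Assumed, because the documents are silent: mean visits, dispersion, and the correlation between dose and health. (The score counts 4 sessions while the main-study section describes 7. Those passages need reconciling, but the argument here does not depend on it.)

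**Step 1: formula.** Let r be the size of a dose–outcome correlation that arises only through health, with no dose effect. For a median split of a normal score, the standardized difference is d = 2 × 0.798r / √[1 − (0.798r)²], and the test statistic is centred at d / √(4/n). For n = 150 and r = 0.10: d = 0.160; √(4/150) = 0.163; centre 0.98; two-sided 5% rejection 16.5%. Likewise r = 0 gives 5%, 0.05 gives 7.8%, 0.15 gives 31.5% and 0.20 gives 51%.

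**Step 2: visit counts.** Gamma-Poisson counts, n = 150, mean 0.6, dispersion 1, no program effect, median split on dose, t-test on 12-month counts, 4,000 simulated arms per row:

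| Correlation of dose with visit propensity | Spurious high-minus-low difference (visits) | False-positive rate |
|---|---|---|
| −0.1 | about −0.08 to −0.09 | about 8–9% |
| −0.2 | −0.17 | 19% |
| −0.3 | −0.26 | 37% |
| −0.4 | −0.35 | about 60% |

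This agrees with Step 1. The count variance is 0.6 + 1 × 0.6² = 0.96 (SD 0.98) and the propensity SD is 0.6, so a propensity correlation of 0.2 shrinks to about 0.2 × 0.6/0.98 = 0.12 with the count itself. That falls between the 0.10 and 0.15 results above. Varying the mean from 0.3 to 1.0 and the dispersion from 0.5 to 2, a correlation of −0.3 gives 16% to 53%.

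**Step 3: change scores.** The plan does not say whether the strata are compared on 12-month levels or on change. In the same model with a stable propensity, the spurious difference in change is about 0 and rejection is 5%. With an assumed baseline-to-follow-up correlation of 0.7 in propensity, it is about −0.06 to −0.10 for correlations of −0.2 to −0.4, with 5–8% rejection. Deterioration during follow-up that also reduces attendance is not modelled and could add to this.

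**Step 4: adjustment and the randomized contrast.** A second model used the 0–7 score split at 5 or more, Poisson visits with mean 0.8 driven by latent health, and n = 188:

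| Dose–health correlation | t-test | Chi-square | Adjusted for baseline visits |
|---|---|---|---|
| 0 | 5.2% | 4.7% | 5.5% |
| 0.3 | 31.9% | 23.2% | 17.5% |
| 0.5 | 71.6% | 53.3% | 42.2% |

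With correlation 0.5 but no link from health to outcome, the t-test stays at 5%. The between-arm test, which is also the test of a zero complier effect, rejects in 4.2% to 5.6% of runs across all scenarios, and the complier estimate averages within 0.01 of zero.

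**The case against.** The strongest reply is that the plan already deals with this. The strata comparison is optional, its verb is *describe*, and the next sentence commits to a randomization-based complier-average analysis. Eligibility requires the ability to travel, and screening at the medical center excludes a prognosis of a year or less; both may narrow health-driven non-attendance. Sessions occupy 7 of 52 weeks (7/52 = 13%), so admissions can block attendance only briefly.

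Much of that stands. The analysis is secondary and permissive, and the route through admissions is plausible but not quantified. But being optional does not make the stated interpretation right. The instrumental-variable analysis answers a different question and does not correct the within-arm test, and the plan does not say which takes precedence if they disagree.

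Three stronger readings are tempting and are not supported:

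- *The test will show a false dose effect.* The documents give no dose–health correlation. The false-positive rate starts at the nominal 5%, and the direction reverses if sicker participants engage more.
- *The spurious difference exceeds the 0.15 the trial is designed to detect.* That target is a difference in change, while the larger figures above are differences in 12-month counts. On change scores under the stated assumptions the bias stays below 0.15.
- *The main result is compromised.* The between-arm analyses and the sample size do not use the dose score.

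**Conclusion.** The point holds as a defect in one optional, secondary analysis. As worded, it attributes to dose a difference that may come from who attends, and it names no adjustment or caveat. On 12-month counts, under the assumptions of Step 2, the spurious difference is about −0.08 to −0.35 visits and the false-positive rate about 8% to 60% for correlations of −0.1 to −0.4. If the comparison is made on change, the bias is much smaller. Every correlation, mean and dispersion here is assumed, so these figures show what could happen and do not predict it. Adjustment for baseline visits reduces the problem but does not remove it, so an adjusted result is still an association. The primary randomized comparison is unaffected. The wording should be changed before the analysis is run.

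**What to change.** In the dose paragraph:

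1. Delete the clause that gives the impact of dose as the purpose of the comparison.
2. Either drop the t-test and chi-square comparison of strata, or replace it with a regression of the outcome on dose score, adjusted for the baseline value of the outcome and the risk-score stratum. State whether the outcome is the 12-month value or the change. Report it as an exploratory association that may reflect self-selection.
3. Keep the frequencies and mean dose scores as descriptive summaries.
4. Reserve causal statements about participation for the complier-average analysis, and state its assumption that participants below the cut-off receive no benefit. That cannot be expected to hold at both planned cut-offs of a multi-point score.

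The cost is a few sentences of plan text. No new data are needed, since baseline utilization and the risk score are already collected, and neither the sample size nor the primary analysis changes.
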